6.1.1. Adverse Events

The verbatim terms used in the CRF by investigators to identify AEs will be coded using the Medical Dictionary for Regulatory Activities (MedDRA). These coded AE terms are referred to as preferred terms (PT); classification into System Organ Class (SOC) is a result of the coding process.

Category	Analysis	Sorted By	Drug-Related TEAE
General	Overall summary		✓
	TEAEs	SOC+ PT+ toxicity grade;	✓
	Serious TEAEs	SOC+ PT	✓
	Grade 3 or worse TEAE	SOC+ PT	✓
	TEAEs leading to treatment discontinuation	SOC+ PT	✓
	TEAEs leading to death	SOC+PT	✓

Category	Analysis	Sorted By	Drug-Related TEAE
	TEAEs leading to dose modification or interruption	SOC+ PT	✓
	AEs of clinical importance	SOC+PT + toxicity grade	
	AEs of special interest	SOC+ PT+ toxicity grade	
	Other safety observations (e.g. other malignancies, eye disorder)	PT + toxicity grade	
	Deaths within 30 days of last dose	Reason for death	

6.1.2. All Adverse Events

Treatment-emergent AEs (TEAEs) are defined as 1) those that first occur in TEAE period (defined as the time from first dose date through 30 days after last dose date, or day before subsequent anticancer therapy, whichever occurs first); 2) present before first dose, but worsened in toxicity grade during TEAE period; 3) had missing start date and its end date is during the TEAE period; 4) was a drug-related event. To determine TEAE, partially missing AE start dates will be imputed according to the rules stated in section 2.6.

Treatment-emergent AEs will be summarized by system organ class and preferred terms, by NCI toxicity grade, by relationship to erdafitinib, and by action taken.

The severity of AEs will be graded on a scale of 1 to 5 according to the adult NCI Common Terminology Criteria for Adverse Events (NCI-CTCAE version 5.0 or higher) where higher grades indicate events of higher severity.

For each TEAE, the percentage of subjects who experience at least 1 occurrence of the given event will be summarized. Tables will be sorted by frequency in incidence (the highest to lowest incidence).

For subjects using strong CYP3A inhibitor during treatment-emergent period, all TEAEs will be summarized by SOC, PT, maximum severity, and strong CYP3A inhibitor (Yes vs No). For subjects using strong CYP2C9 inhibitor during treatment-emergent period, all TEAEs will be summarized by SOC, PT, maximum severity, and strong CYP2C9 inhibitor (Yes vs No).

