6.5.3. Precautions for Concomitant Medications

The following precautions are advised:

• Based on in vitro data, erdafitinib is metabolized by cytochrome CYP2C9 and CYP3A4. A clinical drug-drug interaction study showed that on average, erdafitinib exposure (C_{max} and AUC) was increased 5% and 34%, respectively, when co-administered with itraconazole (a strong inhibitor of CYP3A4) and 21% and 48%, respectively, when co-administered with fluconazole (a moderate inhibitor of CYP2C9). For this reason, strong CYP3A4 and moderate CYP2C9 inhibitors should be used with caution (see Section 10.10). Consider alternative therapies with no or minimal CYP2C9 or CYP3A4 inhibition potential during treatment with erdafitinib. If co-administration of a moderate inhibitor of CYP2C9 or strong inhibitor of CYP3A4 is unavoidable, monitor the subject closely for adverse reactions and consider dose modifications accordingly. If the strong inhibitor is discontinued, the erdafitinib dose may be increased in the absence of drug-related toxicity.

Based on in vitro data, erdafitinib is metabolized by cytochrome CYP2C9 and CYP3A4. The impact of moderate CYP2C9 inducers and strong CYP3A4 inducers (such as rifampin) on erdafitinib was not clinically studied. The concomitant use of these agents with erdafitinib should be avoided (see Section 10.10).

Co-administration of erdafitinib with moderate CYP3A inducers may decrease erdafitinib exposure. Caution should be exercised for concomitant administration of erdafitinib and these agents (see Section 10.10). A comprehensive list of CYP3A4/2C9 inducers is provided in Section 10.10 and in http://medicine.iupui.edu/CLINPHARM/ddis/main-table; however, both these references may not be exhaustive and up-to-date at any given time. Please consult the product information of ongoing and new concomitant medications for the most accurate information on potential strong inducers of CYP3A4 and CYP2C9.

- Until further data become available, concomitant use of erdafitinib with CYP3A4 substrates with narrow therapeutic indices should be avoided.

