Grade 2	 Consider holding erdafitinib if the subject has other study-drug related concomitant Grade 2 AEs. Hold erdafitinib if the subject was already on symptom management (dexamethasone solution swish and spit and lidocaine 2%-5% jelly or solution) for more than a week. If the erdafitinib is withheld, reassess in 1-2 weeks. If this is the first occurrence of toxicity and resolves to ≤Grade 1 or baseline within 2 weeks, restart at same dose. If recurrent event or takes >2 weeks to resolve to ≤Grade 1 or baseline, then restart at 1 dose level below. 	 Dexamethasone solution (0.5 mg/5mL solution) swish and spit QID or similar solution that is available in your country/territory and lidocaine 2-5% jelly or solution. Consider concomitant etiologies such as oral candidiasis, oral herpes and recommend appropriate anti-fungal or anti-viral agents.

Grade	Study Drug (Erdafitinib) Management	Symptom Management
Grade 3	 Hold erdafitinib, with reassessments of clinical condition in 1-2 weeks. When resolves to ≤Grade 1 or baseline, restart at 1 dose level below in consultation with the medical monitor. 	 Dexamethasone solution (0.5 mg/5mL solution) swish and spit QID or similar solution that is available in your country/territory and lidocaine 2%-5% jelly or solution. Consider pain management strategies. Consider IV hydration.
Grade 4	Discontinue erdafitinib.	Evaluation and therapy as clinically indicated.

 Table 10: Guidelines for the Management of Oral Mucositis

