10.9. Appendix 9: Amsler Grid

Study	Number:		_
-------	---------	--	---

Subject ID: _____

Date:	
Date.	_

Examiner:

-	1111			1111111				1		11
-		++-			-		++	-		
+				+	-		++	-		
-					-		+ +	-		
		1.1		1.1	2			1.111		1.1
			1-1-1-				1.1			
	1-1-									
-					311					
								-		
-		++						-		
+				+	+			-		+ + -
+		++	++	++	-		++	-		
-				+ +	-		+	-		+ + -
_								-		+
_										
									-	
-				++	-			-		
+				++	-		++	+		
								_		

10.10. Appendix 10: Drugs Classified as Strong or Moderate In Vivo Inhibitors and Inducers of CYP3A4/2C9 Enzymes

Strong	CYP3A4	Inhibitors	
--------	--------	------------	--

Boceprevir	Conivaptan
Clarithromycin	Indinavir
Grapefruit juice	Itraconazole
Lopinavir	Ketoconazole
Mibefradil	Ritonavir
Nefazodone	Nelfinavir
Posaconazole	Conivaptan
Saquinavir	Boceprevir
Telaprevir	Clarithromycin
Telithromycin	Erythromycin
Voriconazole	Troleandomycin
Fluconazole	

Strong Inhibitors: ≥5-fold increase in AUC or >80% decrease in CL.

Moderate to Strong CYP3A4 Inducers Moderate CYP3A4 Inducers						
Bosentan Efavirenz						
Etravirine	Modafinil					
Nafcillin	Lersivirine					
Talviraline	Tipranavir					
Lopinavir						
S	trong CYP3A Inducers					
Avasimibe	Carbamazepine					
Barbiturates eg, phenobarbital	Phenytoin					
Rifabutin	Rifampin					
St. John's wort Mitotane						
Enzalutamide	Apalutamide					

Madawata ta Stuana CVD2 & 4 Induaawa

Strong Inducers: ≥80% decrease in area under the curve (AUC). Moderate Inducers: 50% to 80% decrease in AUC.

Moderate CYP2C9 Inhibitors

Fluconazole	Amiodarone
Miconazole	Piperine
Oxandrolone	Atacigual
Tienilic acid	Azapropazone
Bucolome	Sulfaphenazole
Benzbromarone	

Moderate CYP2C9 Inducers

Carbamazepine	Rifampin
Enzalutamide	Aprepitant

Reference: University of Washington's Drug Interaction Database

http://www.fda.gov/Drugs/DevelopmentApprovalProcess/DevelopmentResources/DrugInteractionsLabeling/ucm093664.htm#4

Both these references may not be exhaustive and up-to-date at any given time. Please consult the product information of ongoing and new concomitant medications for the most accurate information on potential moderate to strong inhibitors or inducers of CYP3A4 and CYP2C9.

CONFIDENTIAL – FOIA Exemptions Apply in U.S.

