6. SAFETY

All safety analyses will be based on the safety analysis set, unless otherwise specified.

Safety will be analyzed using the incidence and severity of AEs, physical examinations, vital signs, electrocardiogram (ECG) measurements, clinical safety laboratory assessments, ophthalmologic examinations, performance status and Bone-related Assessments (for adolescents only).

For all continuous safety variables, descriptive statistics will include the N, mean, standard deviation, median, minimum, and maximum. Categorical variables will be summarized using frequency counts and percentages.

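### SAP 6.1.2 splits TEAEs by strong CYP inhibitor use, Yes or No, without tying event onset to inhibitor dates, so the table can show excess toxicity with inhibitors when there is none

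*SAP*

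**What the plan says.** SAP 6.1.2 introduces the table with the words "For subjects using strong CYP3A inhibitor during treatment-emergent period" and then states that "all TEAEs will be summarized by SOC, PT, maximum severity, and strong CYP3A inhibitor (Yes vs No"). The next sentence repeats this for strong CYP2C9 inhibitors.

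Three other statements determine how the table would be built:

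- The treatment-emergent period is "defined as the time from first dose date through 30 days after last dose date, or day before subsequent anticancer therapy, whichever occurs first" (SAP 6.1.2).
- The counting unit is the subject: "the percentage of subjects who experience at least 1 occurrence of the given event will be summarized" (SAP 6.1.2).
- The output is descriptive: "Categorical variables will be summarized using frequency counts and percentages" (SAP 6).

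Neither document says whether Yes/No describes the subject or the event. Neither says what happens to an event that starts before the inhibitor or after it has stopped. SAP 2.6 does provide for start and end dates of concomitant therapies and for AE onset dates, with imputation rules for partial dates.

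**The concern.** The sentence classifies subjects, the counting unit is the subject, and maximum severity is a per-subject summary over the whole period. The natural reading is therefore ever-user against never-user. Two biases follow, both upward.

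1. **Ordering and reverse causation.** A user's events before the first inhibitor dose count under Yes. Some may be the reason for the prescription. For Grade 2 oral mucositis, Protocol Table 10 tells sites: "Consider concomitant etiologies such as oral candidiasis, oral herpes and recommend appropriate anti-fungal or anti-viral agents". Protocol Appendix 10 lists fluconazole, itraconazole, ketoconazole, posaconazole and voriconazole as strong CYP3A4 inhibitors. Stomatitis is common with this drug: 39% and 58% in the two earlier studies in Protocol 2.2.1.
2. **Time on drug.** A subject treated for longer has more time to start an inhibitor and more time to have any TEAE. The Yes column selects such subjects, and a percentage of subjects does not correct for it.

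At stake is the only pair of AE tables in the SAP split by inhibitor use. The risk behind them is the one in Protocol 6.5.3, where itraconazole raised erdafitinib AUC by 34% and Cmax by 5%. A bias of moderate size could mimic or obscure the effect of an exposure change that small.

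**Working it through.** The plan gives no figure for this table, so there is nothing to reproduce. The calculations below ask what a subject-level split would show if inhibitors had **no** effect on toxicity. All hazards and prescribing rates are assumptions; only the stomatitis percentages come from the documents.

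**1. Duration alone, constant hazards.** Let time on drug be exponential with rate d, and let the TEAE hazard a and inhibitor hazard i be constant and independent.

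- P(TEAE) = a/(a+d) = 0.30, so a = 0.4286d.
- P(user) = i/(i+d) = p, so i = d·p/(1−p).
- P(neither) = d/(d+a+i).
- P(both) = 1 − 0.70 − (1−p) + P(neither).

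| p | P(neither) | P(both) | TEAE in Yes = P(both)/p | TEAE in No = (0.30 − P(both))/(1−p) |
|---|---|---|---|---|
| 0.05 | 0.6751 | 0.0251 | 50.3% | 28.9% |
| 0.10 | 0.6495 | 0.0495 | 49.5% | 27.8% |
| 0.15 | 0.6230 | 0.0730 | 48.7% | 26.7% |

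The rate d cancels, so trying different median durations is not a sensitivity check here. The shape of the TEAE hazard is what matters.

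**2. Duration alone, early onset.** Keep 30% TEAE and 10% users, but confine the TEAE hazard to the first c months, with median time on drug of 3 to 6 months.

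| c (months) | Yes | No | Gap (points) |
|---|---|---|---|
| 1 | 32-33% | 30% | about 2-3 |
| 2 | 33-36% | 29-30% | about 3-6 |
| 3 | 35-38% | 29-30% | about 5-9 |

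**3. Reverse causation alone.** Let s be stomatitis incidence (0.39 or 0.58, Protocol 2.2.1). Assume a listed antifungal is given to a fraction r of those with stomatitis (0.10 or 0.15) and to 0.05 of the rest.

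- Stomatitis in Yes = s·r / [s·r + (1−s)·0.05].
- Stomatitis in No = s(1−r) / [s(1−r) + (1−s)·0.95].

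| s | r | Yes | No | Gap (points) |
|---|---|---|---|---|
| 0.58 | 0.10 | 0.058/0.079 = 73.4% | 0.522/0.921 = 56.7% | 17 |
| 0.58 | 0.15 | 0.087/0.108 = 80.6% | 0.493/0.892 = 55.3% | 25 |
| 0.39 | 0.10 | 0.039/0.0695 = 56.1% | 0.351/0.9305 = 37.7% | 18 |
| 0.39 | 0.15 | 0.0585/0.089 = 65.7% | 0.3315/0.911 = 36.4% | 29 |

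The gap here is a direct consequence of the assumed r against 0.05.

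**4. Does splitting by time remove the bias?** This was simulated with 400,000 subjects in each of 16 settings. Assumed inputs were:

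- exponential time on drug, median 3 or 6 months, plus one month;
- 12-month AE risk of 30% or 60%;
- inhibitor start hazard of 0.01 or 0.03 per month (5% to 32% become users), the inhibitor continuing once started;
- that hazard either unchanged or tripled after the AE.

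| Result | AE does not prompt the inhibitor | AE triples its hazard |
|---|---|---|
| Risk ratio, user against non-user | 1.48-1.76 | 1.98-3.08 |
| Share of users' first events that came before the inhibitor | 50-60% | 68-80% |

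Assigning events and person-time by whether they fall before or after inhibitor start gives rate ratios of 0.99 to 1.03 across all 16 settings. The true value is 1.00.

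**The case against.** The strongest reply is that the defect is inferred. Read literally, the SAP sentence covers only users, so a subject-level No column would be empty. Yes/No might then be an on/off flag for each event, which would largely avoid the problem. This stands as far as it goes: the flag is undefined. But an event-level reading needs an onset window and a time-at-risk denominator, and the SAP gives neither. Either reading calls for the same repair.

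The antifungal path is also less direct than it may look. The Grade 1 row of Protocol Table 10 names clotrimazole and nystatin, neither of which is on the strong-inhibitor list. The Grade 2 text names no agent. Protocol 6.5.3 asks sites to consider alternatives with little or no inhibition. Reverse causation is therefore plausible but not established.

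The sizes depend on assumptions, and the early-onset case cuts the duration gap to 2-9 points. Early onset is credible for at least the phosphate effect, since Protocol 4.3 places peak serum phosphate at week 6. SAP 4.6 also counts medications begun before the first dose and continued. Subjects already on an inhibitor at first dose bring neither bias.

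Finally, the table is descriptive and does not carry the interaction question alone. An interaction study has measured the exposure change, and exposure-safety analyses may be explored (Protocol 3 and 9.4.4, SAP 7). That limits the consequence. It does not remove the bias, because readers will compare the two columns.

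**Conclusion.** The point holds as a risk created by an undefined flag. With no onset rule, and on the natural ever/never reading, the table can show excess toxicity with inhibitors when there is none. Both mechanisms push upward, but their size cannot be derived from the documents. Duration alone gives about 49-50% against 27-29% under constant hazards, with 30% TEAE and 5-15% users. It gives about 2-9 points if onset is confined to the first 1-3 months, with 10% users. The 17-29 points for reverse causation rest wholly on assumed prescribing rates.

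A reader might infer three stronger things, and the documents support none of them:

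- **That the SAP directs pre-inhibitor events into Yes.** It does not say so; it is silent.
- **That inhibitor use at any time counts.** Use is limited to the treatment-emergent period.
- **That a false signal is certain.** Protocol 6.5.3 tells sites to "monitor the subject closely for adverse reactions and consider dose modifications accordingly" when an inhibitor is unavoidable, which could move the contrast the other way.

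The primary endpoint, alpha and sample size are unaffected. This is a cheap improvement to a supportive safety table.

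**What to change.** In SAP 6.1.2, define the flag for each event:

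- Count a TEAE as with inhibitor only if its onset or grade worsening falls between the recorded inhibitor start and its stop plus a stated carry-over. Protocol 2.2.1 gives an erdafitinib half-life above 50 hours, which is relevant to that choice.
- Count all other on-treatment events and time as without inhibitor. This includes users' time before the inhibitor and all time of never-users.
- Report exposure-adjusted rates for each category beside the percentages.
- State a tie rule for imputed dates. SAP 2.6 sets a missing day to the 15th and a missing day and month to 30 June, and applies the AE rule to concomitant medication. An event and an inhibitor in the same month can therefore receive the same date.
- Apply the same definition to the CYP2C9 table.

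The cost is SAP wording and programming. SAP 2.6 already handles the dates, so no new data collection is foreseen. The downsides are smaller with-inhibitor cells and some reliance on imputed dates for the order of events.

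### The SAP splits adverse events by strong CYP2C9 inhibitor use, while the protocol's precaution and drug list concern moderate CYP2C9 inhibitors, so users of those drugs are counted as unexposed in that table

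*SAP*

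**What the plan says.** SAP Section 6.1.2 plans two drug-interaction summaries of treatment-emergent adverse events (TEAEs). The first opens "For subjects using strong CYP3A inhibitor during treatment-emergent period" and splits Yes versus No. The second opens "For subjects using strong CYP2C9 inhibitor during treatment-emergent period" and states that "all TEAEs will be summarized by SOC, PT, maximum severity, and strong CYP2C9 inhibitor (Yes vs No"). The SAP plans no summary by use of a moderate CYP2C9 inhibitor.

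Protocol Section 6.5.3 pairs the classes differently: "strong CYP3A4 and moderate CYP2C9 inhibitors should be used with caution". It repeats the pair in its monitoring text: "If co-administration of a moderate inhibitor of CYP2C9 or strong inhibitor of CYP3A4 is unavoidable, monitor the subject closely for adverse reactions".

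Protocol Appendix 10 (Section 10.10) lists strong CYP3A4 inhibitors. For CYP2C9 it has a single inhibitor list, headed "Moderate CYP2C9 Inhibitors".

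SAP Section 4.6 codes concomitant medications to WHO-DD generic terms and presents them by ATC class. Neither it nor Section 6.1.2 says which list or database decides whether an inhibitor is strong or moderate.

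**The concern.** The CYP3A table uses the class the protocol warns about. The CYP2C9 table does not. A programmer who follows SAP 6.1.2 literally will put every subject on a moderate CYP2C9 inhibitor in the comparator group, so the subjects of interest dilute the very group they should be compared with.

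The protocol treats reduced CYP2C9 activity as a safety matter. Section 6.5.3 reports a larger AUC increase with the moderate CYP2C9 inhibitor studied than with the strong CYP3A4 inhibitor studied. Section 6.1 predicts 50% higher exposure in subjects with the CYP2C9 *3/*3 genotype and asks for monitoring of adverse reactions in them. A reader of the study report who sees an empty or nearly empty 'Yes' column could conclude that no relevant CYP2C9 inhibition occurred, when the table had only looked for a different class.

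**Working it through.** There is no power, alpha or sample size figure to reproduce. The check is a comparison of texts and a count of the lists in Appendix 10.

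**Step 1: the classes, side by side**

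| Enzyme | SAP 6.1.2 table | Protocol 6.5.3 precaution and monitoring | Match |
|---|---|---|---|
| CYP3A / CYP3A4 | strong | strong | yes |
| CYP2C9 | strong | moderate | no |

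**Step 2: count of CYP2C9 inhibitors in Appendix 10**

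- Moderate: fluconazole, amiodarone, miconazole, piperine, oxandrolone, atacigual, tienilic acid, azapropazone, bucolome, sulfaphenazole, benzbromarone. Total 11.
- Strong: none named. Total 0.

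**Step 3: overlap with the strong CYP3A4 list**

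Fluconazole is the only one of the 11 that also appears there. That leaves 11 − 1 = 10 drugs.

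**Step 4: where each user lands, assuming Appendix 10 decides the class**

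| Subject takes | CYP2C9 table | CYP3A table |
|---|---|---|
| Fluconazole | No | Yes |
| One of the other 10, no strong CYP3A4 inhibitor | No | No |
| One of the other 10, plus a strong CYP3A4 inhibitor | No | Yes |

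On this assumption the 'Yes' column of the CYP2C9 table has 0 subjects. With a different source the column might hold some subjects. Any drug that source classes as moderate would still go to 'No', so the misplacement of moderate users does not depend on the assumption.

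**Step 5: measured interactions in protocol 6.5.3**

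| Co-administered drug | Class given there | Cmax | AUC |
|---|---|---|---|
| Itraconazole | strong CYP3A4 inhibitor | +5% | +34% |
| Fluconazole | moderate CYP2C9 inhibitor | +21% | +48% |

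The AUC increase with the moderate CYP2C9 inhibitor is larger by 48 − 34 = 14 percentage points. These are the only two inhibitor effects on erdafitinib that the section reports.

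**The case against.** The case for leaving this alone has several parts.

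- **The protocol does recognise strong CYP2C9 inhibitors.** The title of Appendix 10 covers strong and moderate inhibitors of both enzymes, and its closing note mentions moderate to strong inhibitors of CYP2C9. This stands. A reader might infer that the SAP uses a class foreign to the protocol, and that goes too far. The protocol refers to the class in general terms but names no drug in it and sets no precaution for it.
- **The table need not be empty.** Appendix 10 warns that its references may be incomplete or out of date and sends readers to product information. The SAP does not adopt it as the source. This stands too: an empty 'Yes' column is conditional, and even then the 'No' column is populated.
- **The subjects with the measured 48% effect are not lost.** Under Appendix 10, fluconazole users are 'Yes' in the CYP3A table. This stands, with the limit that they are mixed there with users of other strong CYP3A4 inhibitors and remain in the CYP2C9 'No' group. It would be wrong to infer that the plan misses the subjects with the largest measured interaction altogether.
- **The remaining gap is unmeasured.** For the other 10 drugs the documents give neither a measured effect on erdafitinib nor an expected number of users. The 48% cannot be carried over to them. This stands.
- **Other analyses help.** SAP 4.6 keeps users identifiable by generic term. Protocol 9.4.4 and SAP Section 7 allow exposure to be explored against TEAEs. The exposure analysis is optional, and neither provides the split that SAP 6.1.2 intends.

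None of this explains why the CYP2C9 table should use a class other than the one under the protocol's precaution.

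**Conclusion.** The mismatch is real, and SAP 6.1.2 is wrong as written on this line. Followed literally, it counts users of moderate CYP2C9 inhibitors as unexposed in the one table meant to examine CYP2C9 inhibition.

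The size is small. The table is a descriptive, non-randomised safety split that tests no hypothesis. The primary endpoint, error control, futility rules and the general TEAE tables are untouched. The number of subjects affected cannot be derived from the documents and may be low.

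Two statements rest on the assumption that Appendix 10 decides the class: that the 'Yes' column has no subjects, and that users of 10 of the 11 drugs are 'No' in both tables unless they also take a strong CYP3A4 inhibitor. The mismatch of classes does not rest on it.

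**What to change.** In SAP 6.1.2, change the CYP2C9 split to moderate or strong CYP2C9 inhibitor (Yes versus No), so that it covers the class in protocol 6.5.3 and any strong inhibitor that occurs. State the classification source: Appendix 10 with any updates at the time of analysis. The source has to be named because Appendix 10 lists no strong CYP2C9 inhibitor and describes its references as possibly incomplete. Keep the strong CYP3A table as it is.

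The cost is a change of wording and a code list mapped to the WHO-DD generic terms already planned in SAP 4.6. It needs no new data and changes no clinical instruction.
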